[Part 2 of 2 of the document. The other parts are not shown.]

#### **5.4.2.3. Distribution of percentages of serogroup B invasive disease strains killed**

Not applicable

#### **5.4.2.4. Immune response of MenABCWY, rMenB+OMV NZ and MenACWY**

Not applicable

### **5.5. Safety and reactogenicity**

#### **5.5.1. Analysis of safety and reactogenicity planned in the protocol**

Distribution of subjects by vaccinations will be summarised by vaccine group for the Enrolled Set. In case of vaccination error, subjects will be analyzed “as treated” (according to the vaccine the subject received).

**Analysis sets:** Solicited Safety Set (solicited local and systemic adverse events and other solicited adverse events), Unsolicited Safety Set (unsolicited adverse events), and Overall Safety Set.

**CONFIDENTIAL**

205416 [MENB REC 2ND GEN-038 (V72\_72)]

Statistical Analysis Plan Amendment 5

Endpoint	Statistical Analysis Methods
Primary	
Endpoints description: The frequencies and percentages of subjects with solicited local (i.e., injection site pain, erythema, swelling, induration) and systemic (i.e., fever [temperature <math>\geq 38.0^{\circ}\text{C}</math>], nausea, fatigue, myalgia, arthralgia, headache) adverse events during the 7 days (including the day of vaccination) following each vaccination at Day 1, Day 61 and Day 181.
 
All solicited adverse events will be summarised according to defined severity grading scales, see protocol section 12.5.9.3.
 
Frequencies and percentages of subjects experiencing each adverse event will be presented for each symptom severity. Summary tables showing the occurrence of any local or systemic adverse event overall and at each time point will also be presented.
 
Post-vaccination solicited adverse events reported from Day 1 to Day 7 will be summarised for the intervals Day 1-3, Day 4-7, and Day 1-7 by maximal severity and by vaccine group, excluding the 30-minute measurement, which will be summarised separately. The severity of solicited local adverse events, including redness (erythema) at injection site, swelling of skin at injection site, and hardness of skin at injection site will be summarised according to categories based on linear measurement: None (1 to 24mm); Mild (25 to 50mm); Moderate (51 to 100mm); Severe (<math>>100\text{mm}</math>).
 
Injection site tenderness and systemic reactions (except fever) occurring up to 7 days after each vaccination at Day 1, Day 61 and Day 181 will be summarised according to "mild", "moderate" or "severe".
 
Each solicited local and systemic adverse event will also be further summarised as "none" versus "any" (for fever the latter will be <math>\geq 38.0^{\circ}\text{C}</math>).
 
Use of antipyretics and analgesics will be summarised by frequency by type of use (prophylactic versus treatment) and percentage of subjects reporting use.
 
Body temperature will be summarised by <math>0.5^{\circ}\text{C}</math> increments from <math>36.0^{\circ}\text{C}</math> up to <math>\geq 40^{\circ}\text{C}</math> and will be broken down according by route of measurement, if applicable. Frequencies and percentages of subjects with temperatures <math>\geq 38.0^{\circ}\text{C}</math> and temperatures <math>\geq 40.0^{\circ}\text{C}</math> will also be presented.

	
Endpoints description: The frequencies and percentages of subjects with any unsolicited AEs (including all SAEs), AEs leading to withdrawal and medically attended AEs during the 7 and the 30 days (including the day of vaccination) following each vaccination at Day 1, Day 61 and Day 181.
 
The frequencies and percentages of subjects with SAEs, AEs leading to withdrawal, AESIs and medically attended AEs throughout the study period.
 
This analysis applies to all adverse events occurring during the study, judged either as possibly related, or not related to vaccination by the investigator, recorded in AE CRF, with a start date on or after the date of first vaccination. AE starting prior to the first vaccination will only be listed.
 
The original verbatim terms used by investigators to identify adverse events in the CRFs will be mapped to preferred terms using the MedDRA dictionary. The adverse events will then be grouped by MedDRA preferred terms into frequency tables according to system organ class.
 
All reported adverse events, as well as adverse events judged by the investigator as possibly related to study vaccine, will be summarised according to system organ class and preferred term within system organ class. These summaries will be presented by vaccine group and by interval of study observation. When an adverse event occurs more than once for a subject, the maximal severity and strongest relationship to the vaccine group will be counted.
 
Separate summaries will be produced for the following categories:
 
 
• Serious adverse events.
 
• Adverse events that are possibly related to vaccine.
 
• Adverse events of special interest.
 
• Adverse event leading to withdrawal.
 
• Adverse events leading to a medically attended visit.
 
 
Data listings of all adverse events will be provided by subject. In addition, adverse events in the categories above will be provided as listed data.
 
Local and systemic AEs will be analyzed by point estimates with associated 95% CIs [Clopper, 1934].

### **5.5.2. Additional considerations**

For analyses of the safety and reactogenicity endpoints, subjects will be analyzed “as treated” according to the actual vaccination a subject received.

For participants who have more than one solicited local (i.e., injection site pain, erythema, swelling, induration) or systemic (i.e., fever [temperature  $\geq 38.0^{\circ}\text{C}$ ], nausea, fatigue, myalgia, arthralgia, headache) measurement on a day, all data is listed. For the analysis, the worst measurement is analyzed. For example, if for a participant a temperature of  $38.5^{\circ}\text{C}$  and  $39.0^{\circ}\text{C}$  is recorded on one day, both values get listed, for the analysis the  $39.0^{\circ}\text{C}$  is analyzed.

Analyses of safety objectives will be repeated by age group (10-17 years of age and 18-25 years of age), race, sex, region (US/ ex-US), and with and without a previous MenACWY vaccination (primed and unprimed).

[figure not shown]
A Table and Listing of COVID-19 AE cases will be provided.

In case for a subject besides ediary data, also solicited reactions were recorded in the CRF, the CRF data will be mapped into the SDTM data with the ediary data (FA domain). For the analysis, the CRF data will be used in case of duplicate data.

## **6. ANALYSIS INTERPRETATION**

Multiple objectives and endpoints require type I error control. Full alpha (0.05) is split equally ( $\alpha=0.025$ ) between rMenB+OMV NZ objectives and MenABCWY objectives. Furthermore, within rMenB+OMV NZ, as well as within MenABCWY, objectives are tested hierarchically. If the first null hypothesis is rejected, then the testing will continue with the second hypothesis at same alpha. Same for 3rd, 4th, and so forth. Whenever a null hypothesis is not rejected, then the testing will stop.

As the comparator for MenABCWY non inferiority objective for the B component will be the selected schedule of rMenB+OMV NZ as determined in this study, the objectives of rMenB+OMV NZ will be analysed first. Additionally, if all null hypotheses related to rMenB+OMV NZ objectives will be rejected, the alpha ( $\alpha=0.025$ ) will be propagated to the MenABCWY part, and hypotheses related to MenABCWY objectives will be tested at full alpha ( $\alpha=0.05$ ). See Figure 2 for an explanation of the hierarchical testing (top to bottom, the order indicated by the arrows).

**Figure 2** Hierarchical testing of hypothesis

\* Alpha split equally between rMenB+OMV NZ and MenABCWY vaccine objectives.

If all rMenB+OMV NZ objectives achieved, MenABCWY vaccine objectives will be tested at full alpha.

\*\* If all objectives of rMenB+OMV NZ are met, the comparator will be the 0,2-months schedule. If the 0,2-months objective is not met, and the 0,6-months is met, then the 0,6-months schedule will be the comparator. If the 0,6-months is also not met, then the 0,2,6-months schedule will be the comparator.

Refer to Glossary of terms for definitions of test-based and responder-based vaccine effectiveness.

## 7. CONDUCT OF ANALYSES

### 7.1. Sequence of analyses

The final study report will contain at least the final analyses of all primary and secondary endpoints.

### 7.2. Statistical considerations for interim analyses

No interim analysis is planned for this study

## **8. CHANGES FROM PLANNED ANALYSES**

Not applicable

## **9. NON-STANDARD DATA DERIVATION RULES AND STATISTICAL METHODS**

The following sections describe additional derivation rules and statistical methods which are not presented in section 10.1.

### **9.1. Data derivation**

Not applicable

### **9.2. Statistical Method**

Not applicable

## **10. ANNEXES**

### **10.1. Business rules for standard data derivations and statistical methods**

This section contains GSK Vaccines' standard rules for data display and derivation for clinical and epidemiological studies.

#### **10.1.1. Attributing events to vaccine doses**

The dose relative to an event is the most recent study dose given to a subject prior to the start of a given event. For example, if the start date of an adverse event is between Dose 1 and Dose 2, the relative dose will be Dose 1.

If an event starts on the same day as a study dose, the relative dose will be derived from the additional information provided in the CRF using the contents of the flag indicating if the event occurred before or after vaccination. If 'after vaccination' is selected, the relative dose for the event will be the one administered on the start day of the event. If 'before vaccination' is selected, the relative dose for the event will be the dose prior to this one.

## **10.1.2. Handling of missing data**

### **10.1.2.1. Dates**

When partially completed dates (i.e. with missing day or month) are used in calculations, the following standard rules will be applied:

- A missing day will be replaced by 15
- A missing day and month will be replaced by June 30th.

The following exceptions apply:

- Adverse event start dates with missing day:
  - If the event starts in the same month as at least one of the study doses, the contents of AE.AESTRTPT (the flag indicating if the event occurred before or after vaccination) will be used to complete the date. If ‘after vaccination’ is selected, the imputed start date will match the first (or only) study dose given during that month. If ‘before vaccination’ is selected, the imputed date will be one day before the first (or only) study dose given during that month.
- Adverse event start dates with missing day and month:
  - If the event starts in the same year as at least one of the study doses, the contents of AE.AESTRTPT (the flag indicating if the event occurred before or after vaccination) will be used to complete the date. If ‘after vaccination’ is selected, the imputed start date will match the first (or only) study dose given during that year. If ‘before vaccination’ is selected, the imputed date will be one day before the first (or only) study dose given during that year.

All other cases of incomplete AE or concomitant medication/vaccination start date will follow the standard rules above.

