**10.1.3.11. Duration of events**

The duration of an event with a start and end date will be the number of days between the start and end dates plus one day, i.e. an event that starts on 03MAR2018 and ends on 12MAR2018 has a duration of 10 days.

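### Imputed adverse event dates are not checked against other recorded dates, so an event proven to lie in a 7- or 30-day window can fall outside it and a derived duration can be negative (minor)

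*SAP*

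**What the plan says.** SAP Amendment 5, section 10.1.2.1, sets two defaults for partial dates used in calculations: "A missing day will be replaced by 15" and "A missing day and month will be replaced by June 30".

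There are two exceptions, both for AE start dates only:
- **Day missing, month contains a study dose.** If flagged as after vaccination, "the imputed start date will match the first (or only) study dose given during that month". If flagged as before vaccination, "the imputed date will be one day before the first (or only) study dose given during that month".
- **Day and month missing, year contains a study dose.** The same logic applies by year. For an event flagged as after vaccination, "the imputed start date will match the first (or only) study dose given during that year".

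The section closes with: "All other cases of incomplete AE or concomitant medication/vaccination start date will follow the standard rules above". Incomplete end dates have no exception, so they take the 15th or 30 June.

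The imputed dates feed three places:
- Section 10.1.3.10 counts onset day from the last vaccination, with the vaccination day as Day 1.
- Section 10.1.3.11 defines duration, in days: "The duration of an event with a start and end date will be the number of days between the start and end dates plus one".
- The primary row of the table in section 5.5.1 reports unsolicited AEs "during the 7 and the 30 days (including the day of vaccination") after the vaccinations at Day 1, Day 61 and Day 181.

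Nothing in the standard rules of section 10.1 limits an imputed date by a recorded start, a recorded end or the last contact. Section 9.1, where study-specific derivations would stand, is marked not applicable.

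**The concern.** A fixed default is acceptable when nothing else is known about a date. Here it also applies when the record already rules the imputed date out. A start known only by month, with a full end date early in that month, can be imputed after the event ended. If the month of onset and the end date together place the onset within 7 or 30 days of a dose, the event is dropped from a window to which it demonstrably belongs. Those windows define percentages in the primary safety row. Similarly, an end date missing its day can be imputed before a known start, and the duration formula then returns zero or a negative number.

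**Working it through.** **Formulas** (sections 10.1.3.10 and 10.1.3.11): onset day = start − dose + 1; duration = end − start + 1.

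**The plan's own example.** Start 3 March 2018, end 12 March 2018: 12 − 3 + 1 = 10 days, as section 10.1.3.11 states.

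**Start in a dose-free month** (constructed dates, non-leap year)
- Dose 10 January, start recorded as February, end 3 February. Possible onsets are 1 to 3 February, Day 23 to 25. The 30-day window ends on 8 February. The imputed start, 15 February, is Day 37. Duration: 3 − 15 + 1 = −11.
- Dose 28 January, start recorded as February, end 2 February. Possible onset is Day 5 or 6. The imputed start is Day 19, outside the 7-day window. Duration: 2 − 15 + 1 = −12.

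**Before-vaccination branch**
- Planned Day 181 to Day 211 spacing: doses 28 January and 27 February, start recorded as February, flagged before vaccination, end 2 February. The imputed start is 26 February, Day 30 after the first of these doses, against a possible Day 5 or 6. It leaves the 7-day window but stays in the 30-day window. Duration: 2 − 26 + 1 = −23.
- Off-schedule doses on 10 January and 20 February (41 days apart), end 3 February. The imputed start is 19 February, Day 41, against a possible Day 23 to 25, so the 30-day window is lost too.

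**Incomplete end dates**
- Start 20 March, end recorded as March: 15 − 20 + 1 = −4.
- Start 10 September, end recorded by year only: 30 June is 72 days before the start, so the duration is −72 + 1 = −71.
- If the start is uniform over the year and the end lies in the same month with its day missing, 185 of 365 start dates (51%) give a duration of zero or less.

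**Enumeration for the windows.** Assumptions: each of 365 dose dates in a non-leap year, onset uniform over the window, start day always missing, no other dose in the onset month. There are 365 × 7 = 2,555 in-window onsets for 7 days and 365 × 30 = 10,950 for 30 days. Of these, 252 and 5,219 fall in a later, dose-free month. The 15th moves 252 of 252 and 1,260 of 5,219 (24%) outside the window. The share that the recorded end date also proves to be in-window depends on an assumed true duration:

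| Duration (days) | 7-day: proven and displaced | Share of 252 | 30-day: proven and displaced | Share of 5,219 |
|---|---|---|---|---|
| 1 | 252 | 100% | 1,260 | 24% |
| 3 | 120 | 48% | 936 | 18% |
| 5 | 36 | 14% | 660 | 13% |
| 7 | 0 | 0% | 432 | 8% |

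As a share of all in-window onsets, the 30-day column runs from 1,260/10,950 = 11.5% to 432/10,950 = 3.9%, and the 7-day column from 252/2,555 = 9.9% to 0%.

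**Scaling by the fraction of missing start days, p.** The SAP does not give p. With p assumed at 1%, 5% or 10% and a 3-day duration, the 30-day loss is 936/10,950 × p = 0.09%, 0.43% or 0.85% of in-window onsets. The 7-day loss is 120/2,555 × p = 0.05%, 0.23% or 0.47%.

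**The case against.** Several stronger readings are tempting, and the SAP does not support them.

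- **That a missing day always becomes the 15th.** It does not. A start in a dose month flagged as after vaccination becomes the dose date, Day 1, and stays in that dose's windows.
- **That 24% and 100% of next-month onsets are provably misplaced.** Those figures count every displaced onset. They equal the provable share only for one-day events, and the provable share falls as duration rises.
- **That the windows are under-counted on balance.** The rule also moves events in. With onsets uniform over the whole month after the dose, the 15th moves 1,259 true in-window onsets out of the 30-day window and 1,516 true out-of-window onsets in. The dose-month exception can also place a Day 8 to 30 onset at Day 1, inside the 7-day window. The record alone does not contradict these inward shifts, but no net loss can be claimed.
- **That reported durations will be impossible.** Sections 5.5.1 and 5.5.2 plan no AE duration summary. Section 10.1.3.11 is a standard derivation, so the negative values matter only if a duration is derived.
- **That imputation after the last contact alters the endpoints.** With Dose 1 on 20 August 2020, Day 211 is 18 March 2021 and Day 541 is 11 February 2022. A start recorded only as 2022 becomes 30 June 2022. The date is impossible, but no 2022 onset lies in a 7- or 30-day window, and no stated upper cut-off removes the event from the whole-study summary.

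These points limit the size of the problem. They do not remove it: a stated rule, followed exactly, can yield a date that the record disproves and change whether an event is in its window.

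**Conclusion.** The point stands at minor severity. Outside the dose-month and dose-year exceptions, within their before-vaccination branch, and for every incomplete end date, section 10.1.2.1 imputes without reference to the other recorded dates. A provably in-window AE can therefore leave the 7- or 30-day window, and a derived duration can be zero or negative.

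The tabulated shares rest on uniform dose and onset dates, a missing start day for every event, a full end date, no other dose in the onset month and the assumed durations. They describe how the rule behaves, not the expected change in a reported percentage. The absolute effect depends on the number of incomplete dates, which the SAP does not give. It is probably small.

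**What to change.** Keep both exceptions in section 10.1.2.1 as they stand and add two sentences:
- After any imputation, a start date later than the recorded end date or the last contact is set to the earlier of these.
- An imputed end date is never earlier than the start date nor later than the last contact.

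The first sentence must act after the exceptions, not replace them. Taking the earliest of the 15th, the end date and the last contact in every case would move an event flagged as after a 25 January dose to 15 January. Section 5.5.1 would then only list it, because it would start before the first vaccination.

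In the first example the start becomes 3 February, Day 25, with a duration of 1 day. All the provable cases in the table return to their window, because there the recorded end date is itself inside it. The cost is two sentences and a small change to the date derivation.

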### **10.1.2.2. Laboratory data**

Missing laboratory results (including immunological data) will not be replaced.

### **10.1.2.3. Daily recording of solicited adverse events**

#### **10.1.2.3.1. Studies with electronic diaries**

For studies using electronic diaries for the collection of solicited adverse events, a solicited adverse events will be considered present only when a daily recording of grade 1 or more is present.

### **10.1.2.4. Unsolicited adverse events**

Unsolicited adverse event summaries are including serious adverse events unless specified otherwise.

**CONFIDENTIAL**

205416 [MENB REC 2ND GEN-038 (V72\_72)]

Statistical Analysis Plan Amendment 5

Missing severity, relationship with study vaccine, and outcome of unsolicited adverse events will not be replaced and will appear as 'UNKNOWN' in all statistical output.

**10.1.3. Data derivation****10.1.3.1. Age at vaccination in days**

When age at vaccination is to be displayed in days, it will be calculated as:

Age = date of vaccination minus date of birth

**10.1.3.2. Age at vaccination in months**

When age at vaccination is to be displayed in months, it will be calculated as the number of complete calendar months between the date of birth (DOB) and the date of vaccination. For example:

DOB = 10JUN2017, Date of vaccination = 09JUL2018 -> Age = 12 months

DOB = 10JUN2017, Date of vaccination = 10JUL2018 -> Age = 13 months

**10.1.3.3. Age at vaccination in years**

When age at vaccination is to be displayed in years, it will be calculated as the number of complete calendar years between the date of birth and the date of vaccination. For example:

DOB = 10SEP1983, Date of vaccination = 09SEP2018 -> Age = 34 years

DOB = 10SEP1983, Date of vaccination = 10SEP2018 -> Age = 35 years

**10.1.3.4. Weight**

Weight will be presented in kilograms. Weights reported in pounds will be converted as follows:

Weight in kilograms = Weight in pounds / 2.2

**10.1.3.5. Height**

Height will be presented in centimeters. Heights reported in feet and inches will be converted as follows:

Height in centimeters = Height in inches x 2.54

### 10.1.3.6. Body mass index (BMI)

BMI will be calculated as follows:

$$\text{BMI} = (\text{Weight in kilograms}) / (\text{Height in meters})^2$$

### 10.1.3.7. Temperature

Temperatures will be presented in degrees Celsius (°C). Temperatures reported in degrees Fahrenheit (°F) will be converted as follows:

$$\text{Temperature (Celsius)} = ((\text{Temperature (Fahrenheit)} - 32) \times 5)/9$$

### 10.1.3.8. Numerical serology results

Numerical serology results will be derived from the content of IS.ISORRES in the SDTM dataset. For assays with a specific cut-off, the following derivation rules apply:

IS.ISORRES	Derived value
“NEG”, “-”, or “(−)”	cut-off/2
“POS”, “+”, or “(+)”	cut-off
“< value” and value is <= assay cut-off	cut-off/2
“< value” and value is > assay cut-off	value
“> value” and value is < assay cut-off	cut-off/2
“> value” and value is >= assay cut-off	value
“value” and value is < cut-off	cut-off/2
“value” and value is >= cut-off	value
All other cases	missing

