### 10.1.3.9. Geometric mean titres (GMTs) and concentrations (GMCs)

Geometric Mean Titre (GMT) or Concentration (GMC) calculations are performed by taking the inverse logarithm of the mean of the log titre or concentration transformations. Antibody titres or concentrations below the cut-off of the assay will be given an arbitrary value of half the cut-off of the assay for the purpose of GMT/GMC calculation. The cut-off value is defined by the laboratory before the analysis and is described in the protocol.

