## **10.3. Glossary of terms**

End of Study (EoS) (Synonym of End of Trial)	For studies with collection of human biological samples and/or imaging data, the EoS is defined as Last subject last visit (T10). or Last testing results released of samples collected at Visit 6*  * In this case EoS must be achieved no later than 8 months after LSLV.
Primary completion date:	The date that the final subject was examined or received an intervention for the purpose of final collection of data for all primary outcomes, whether the clinical trial was concluded according to the pre-specified protocol or was terminated.
Responder-based vaccine effectiveness:	The enc-hSBA methodology involves testing the serum samples from each individual subject against a subset of around 35 strains randomly chosen from the overall panel of 110 meningococcus B US strains. Responder-based vaccine effectiveness is assessed based on the percentage of subjects considered responders, i.e., subjects whose

	serum kills the majority ( $\geq 70\%$ in this study) of the tested strains following vaccination.
Test-based vaccine effectiveness:	The enc-hSBA methodology involves testing the serum samples from each individual subject against a subset of around 35 strains randomly chosen from the overall panel of 110 meningococcus B US strains. Test-based vaccine effectiveness is assessed based on the overall percent of individual positive tests following vaccination and represents the reduction in risk compared to the placebo.

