## CONFIDENTIAL

205416 [MENB REC 2ND GEN-038 (V72\_72)]  
Statistical Analysis Plan Amendment 4**Table 3 Overview of study design: Vaccination and Blood Draw Schedule**

Visits Study Day	Visit 1 Day 1	Visit 2 Day 31	Visit 3 Day 61	Visit 4 Day 91	Visit 5 Day 181	Visit 6 Day 211
Group MenB_0_2_6 N=912	Pre-vacc Blood sample  rMenB+OMV NZ	Post-vacc 1 Blood sample	rMenB+OMV NZ	Post-vacc 2 Blood sample	rMenB+OMV NZ	Post-vacc 3 Blood sample  MenACWY
Group MenB_0_6 N=912	Pre-vacc Blood sample  rMenB+OMV NZ	Post-vacc 1 Blood sample	MenACWY	Post-vacc 2 Blood sample	rMenB+OMV NZ	Post-vacc 3 Blood sample  Placebo
Group ABCWY-1 N=548	Pre-vacc Blood sample  MenABCWY-1	Post-vacc 1 Blood sample	Placebo	Post-vacc 2 Blood sample	MenABCWY-1	Post-vacc 3 Blood sample  Placebo
Group ABCWY-2 N=548	Pre-vacc Blood sample  MenABCWY-2	Post-vacc 1 Blood sample	Placebo	Post-vacc 2 Blood sample	MenABCWY-2	Post-vacc 3 Blood sample  Placebo
Group ABCWY-3 N=548	Pre-vacc Blood sample  MenABCWY-3	Post-vacc 1 Blood sample	Placebo	Post-vacc 2 Blood sample	MenABCWY-3	Post-vacc 3 Blood sample  Placebo
Group ACWY N=150	Pre-vacc Blood sample  MenACWY	Post-vacc 1 Blood sample	Placebo	Post-vacc 2 Blood sample	rMenB+OMV NZ	Post-vacc 3 Blood sample  rMenB+OMV NZ

N = number of subjects; Pre-vacc = pre-vaccination; Post-vacc = post-vaccination

- Treatment allocation: At Day 1, prior to the study vaccination, subjects will be randomised to 1 of the 6 study groups according to a 5:5:3:3:3:1 ratio.
- Blinding: Observer-blind. Kindly refer to Protocol Section 7.3 for details on blinding and unblinding procedures.
- Sampling schedule:
  - A total of 4 blood samples\* will be collected from each subject at Day 1 (pre-vaccination blood sample; approximately 20 mL), at Day 31 (post-vaccination 1 blood sample; approximately 25 mL), at Day 91 (post-vaccination 2 blood sample; approximately 25 mL) and at Day 211 (post-vaccination-3 blood sample; approximately 25 mL).
  - Urine sampling: Urine samples for pregnancy testing will be collected from female subjects of child-bearing potential at Visit 1 (Day 1), Visit 3 (Day 61), Visit 5 (Day 181) and Visit 6 (Day 211) prior to the vaccination.

\* Insufficient blood volume may lead to test cancellation and jeopardise the statistical power. Hence, every effort must be done to collect blood volume as per protocol requirements.

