#### **5.3.1.1. Vaccine effectiveness (Test-based): rMenB+OMV NZ - 3 doses (0,2,6-months schedule)**

Analysis set: Per-protocol set (PPS) will be the primary analysis population

Statistical method: The VE is defined as  $1 - RR = (1 - \text{percentage of samples without bactericidal serum activity at 1:4 dilution in MenB group} / \text{percentage of samples without bactericidal serum activity at 1:4 dilution in the ACWY group}) \times 100\%$  and it will be analyzed using a generalised linear model with vaccine group, strain, and randomization factors (i.e. region (US/ex-US), age category (10-17 YoA/18-25 YoA), previous MenACWY vaccination (y/n)) as independent variables. Furthermore, a repeated statement will be used to estimate the variance of the RR including correlation within subject's responses to different strains. If the statistical model does not converge due to (one of) the factor(s), a model without this/these factor(s) will be fitted instead. The response variable of the model will be the Bernoulli distributed outcome without bactericidal activity at a 1:4 dilution (i.e. response is 1 if titre  $< 4$ , and 0 if titre  $\geq 4$ ), at 1 month after the last vaccination (Month 7) in the MenB group and at Month 1 for the ACWY group. Each subject will contribute with approximately 35 measures to this analysis, each of the measures corresponding to the response variable to one of the 35 strains randomly assigned to be tested with the samples available for that specific subject.

In order to obtain the VE measure which is a measure based on the relative risk (RR), a generalised linear model will be used with the Binary distribution and link function log in order to compute the log RR and the corresponding 97.5% CI. The obtained values will be exponentiated to obtain the RR and the corresponding 97.5% CI. The VE will be computed as  $100\% \times (1 - RR)$ . Effectiveness of rMenB+OMV NZ (0,2,6-months schedule) will be demonstrated if the lower limit of the two-sided 97.5% CI for VE between MenB and the ACWY group is above 65%.

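### Section 10.1.3.8 stores a 'less than' result above the assay cut-off as its full upper limit, so it counts as meeting any threshold equal to that limit and as positive where it is undetermined

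*SAP*

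**What the plan says.** Section 10.1.3.8 of Amendment 5, unchanged from the earlier versions, opens its table with "For assays with a specific cut-off, the following derivation rules apply". Two rows matter here. A result with "< value” and value is <= assay cut-off" becomes half the cut-off. A result with "< value” and value is > assay cut-off" becomes the value itself.

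Section 10.1.3.9 adds: "Antibody titres or concentrations below the cut-off of the assay will be given an arbitrary value of half the cut-off". That covers titres below the cut-off only, and nothing else in the text at hand overrides the second row. On the cut-offs themselves, 10.1.3.9 states: "The cut-off value is defined by the laboratory before the analysis and is described in the protocol".

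The derived values feed these endpoints. The Amendment 5 text at hand starts at 5.4.2.3, so sections 5.3 and 5.4 are cited from Amendment 4.

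- **Enc-hSBA, section 5.3.1.1:** "The response variable of the model will be the Bernoulli distributed outcome without bactericidal activity at a 1:4 dilution". It is 1 for a titre below 4 and 0 for a titre of 4 or more.
- **Responders, sections 5.3.1.2 and 10.3:** "Responder-based vaccine effectiveness is assessed based on the percentage of subjects considered responders". A responder's serum kills at least 70% of about 35 strains. The lower 97.5% limit of the percentage must exceed 65%.
- **4-fold rise, sections 5.3.1.8 and 5.4.1.1:** at least 4 x LOD if baseline is below LOD, 4 x LLOQ if baseline lies between LOD and LLOQ, and otherwise 4 x baseline.
- **Percentage with hSBA at or above LLOQ, and GMTs, section 5.4.1.4.**

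**The concern.** A result reported as below v says that the titre is less than v. Storing it as exactly v assigns a titre that the laboratory has excluded. The table is also uneven: an ordinary censored result is set to half the cut-off, while one censored higher up, and so less informative, gets its full upper limit.

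Because the endpoints use 'at or above' rules, two kinds of error follow. Where the threshold equals v, the result is a known negative and is counted as positive. Where the threshold is below v, the result is undetermined and is always counted as positive.

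At stake are the responder criteria, where no comparator offsets false kills, the 4-fold-rise non-inferiority tests, the LLOQ percentages and the GMTs.

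**Working it through.** The plan states no figure on this point, so there is nothing to reproduce. The check applies the rule and then illustrates its effect.

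**1. The rule applied.** For `<v` with cut-off c, the derived value is c/2 if v ≤ c, and v otherwise. The cut-offs below are assumptions.

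| Cut-off | Result | Derived | Titre ≥4? | ≥LLOQ if LLOQ = 8 | ≥LLOQ if LLOQ = 16 |
|---|---|---|---|---|---|
| 4 | `<4` | 2 | no | no | no |
| 4 | `<8` | 8 | yes | yes | no |
| 4 | `<16` | 16 | yes | yes | yes |
| 8 | `<8` | 4 | yes | no | no |

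- *Certain errors.* With cut-off 4 (taken as the LOD) and LLOQ 8, `<8` is by definition below LLOQ but is derived as 8 and counted as at or above it. With LOD and cut-off 4 and a baseline below LOD, a 4-fold rise needs 4 x 4 = 16. A post-dose `<16` cannot reach that, yet it is derived as 16 and counted.
- *Undetermined but scored positive.* With cut-off 4, `<8` may be below 4 or from 4 to below 8. It is scored as killing.
- *Correct.* With cut-off 4, the ordinary negative `<4` becomes 2.
- *Baseline.* With LOD 4 and LLOQ at most 8, a baseline `<8` derived as 8 requires 4 x 8 = 32, where a subject truly below LOD would need 16.

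**2. Responder criterion, illustrative upper bound.** Inputs: 684 evaluable subjects per MenB group and 3 x 411 = 1233 in the pooled ABCWY group (section 3.3), and the 65% criterion at 97.5% confidence. The Clopper-Pearson lower limit exceeds 65% from 473 of 684 (69.2%) and from 840 of 1233 (68.1%). Let f be the assumed share of subjects affected on most strains, and let every affected non-responder become a responder. A true 65% is then read as 0.65 + 0.35f.

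| f | Read as | False pass, n = 684 | False pass, n = 1233 |
|---|---|---|---|
| 0 | 65.0% | 1.2% | 1.1% |
| 1% | 65.35% | 2.0% | 2.1% |
| 2% | 65.7% | 3.1% | 3.8% |
| 5% | 66.75% | 9.8% | 16.0% |

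**3. The same rule, strain by strain.** At least 25 of 35 strains must be killed, with strains taken as independent. Assume a true kill probability of 0.72, and let a share f of no-activity results be reported as `<8` with cut-off 4. The kill probability is read as 0.72 + 0.28f, and the responder rate is 61.4% at f = 0, 62.8% at 1%, 68.4% at 5% and 74.9% at 10%.

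**4. Test-based VE.** Assume no-activity rates of 20% (MenB) and 80% (ACWY), so VE = 1 − 0.20/0.80 = 75.0%, with f defined as in step 3.

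- Equal f in both groups: the factor (1 − f) cancels and VE stays at 75.0%.
- MenB only: 1 − 0.19/0.80 = 76.3% at f = 5%, and 1 − 0.18/0.80 = 77.5% at f = 10%.
- ACWY only: 1 − 0.20/0.76 = 73.7% at f = 5%, and 1 − 0.20/0.72 = 72.2% at f = 10%.

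**The case against.** The strongest reply is that the document never says such results occur. Enc-hSBA is read at 1:4, and with a cut-off of 4 the ordinary negative is handled correctly. On low volume, section 3.2 says only: "Insufficient blood volume may lead to test cancellation and jeopardise the statistical power". A cancelled test gives no result, not a `<8`. Testing from a higher starting dilution is nowhere described. The cut-offs are left to the protocol and the LOD and LLOQ values are blacked out. If the hSBA cut-off is the LLOQ, `<LLOQ` becomes half the cut-off and is classed correctly. The table is the sponsor's general convention. All of this stands and limits the size of the point. It does not make the row right: the row exists for exactly this case and gives an answer that the result excludes.

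A reader might infer that `<8` is a negative turned into a positive on the primary enc-hSBA endpoint. The documents do not support that. Against a threshold of 4 the result is undetermined. It is a known negative only against thresholds of 8 or more.

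A reader might also infer that the error always favours the vaccine. It does not. At baseline it makes a 4-fold rise harder, and VE can stay the same, rise or fall. The row for `> value` below the cut-off turns undetermined results into negatives.

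Simply setting these results to missing has a flaw of its own. Take a serum that kills 15 strains and reads `<8` on 20. As written it scores 35/35. With the 20 set to missing it scores 15/15 and is still a responder. This objection is accepted and shapes the fix.

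**Conclusion.** The point holds as a defect in a stated rule. A `< value` result above the cut-off is derived as a value it excludes. It is wrongly counted as meeting any threshold equal to that value and is scored positive where it is undetermined. It can inflate the single-arm responder percentage, the percentage at or above LLOQ, post-vaccination 4-fold rise and GMTs.

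The size is unknown, because neither the frequency nor the cut-offs are in this document. The false-pass figures rest on an assumed 1% to 5% of subjects and on converting every affected non-responder, so for that share they are upper bounds and not a forecast. If no such results occur, nothing changes. The change is still worth making, since it is cheap and the rule feeds primary pass/fail criteria.

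**What to change.** Amend the row in section 10.1.3.8:

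- A post-vaccination `< value` result is never counted as meeting a threshold at or above that value.
- Where the threshold lies below the value, score the result in the primary analysis as not meeting it, since no activity was shown. The serum in the example above then scores 15/35 (42.9%) and is a non-responder.
- Add a sensitivity analysis that sets these undetermined results to missing. For the 70% responder rule, it also excludes subjects whose status depends on undetermined strains.
- For 4-fold rise, set a baseline `< value` result above the cut-off to missing.
- For GMT and GMC, use value/2, in line with the half-cut-off convention.
- Report the number of such results by assay, group and visit.

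The cost is a change to one table row, a sensitivity analysis and a count. Responder percentages may be slightly conservative, and slightly fewer 4-fold-rise results will be evaluable.
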